4.7.	Distance ETDRS LogMAR Visual Acuity	
Perform monocular distance ETDRS LogMAR visual acuity test at a 4-meter distance over the test eye only under the following conditions:
 
 dim illumination (e.g., <2.5 lux), low luminance, with high contrast charts (LLHC) bright illumination (e.g., >400 lux), high luminance with low contrast charts (HLLC) 
The Precision Vision 4-meter high contrast ETDRS charts (Chart 1 and Chart 2 OD, Chart 3 and Chart 4 OS) and low contrast ETDRS charts (Chart 1 and 2 OD and Chart 3 and Chart 4 OS) will be used.
 
Two measurements per condition will be performed.
	
4.8.	Subjective Lens Fit Assessment	
Evaluate overall lens fit acceptance (acceptable or unacceptable) based on centration, movement and other fitting characteristics.
 
An unacceptable fit is deemed by one of the following criteria:
 
 limbal exposure at primary gaze or with extreme eye movement edge lift excessive movement in primary and up gaze 	

Visit 4: Treatment 2 Follow-Up Visit			
Step	Procedure	Details	
		
 insufficient movement in all three of the following conditions: primary gaze, up gaze, and Josephson push up 
Note: if lens fit is unacceptable subject will be discontinued from the study.
	
4.9.	Wettability Characteristics	Record the white light lens wettability of both lenses.	
4.10.	Surface Deposits	Record any front and back surface lens deposits.	
4.11.	Lens Damage	Using the slit lamp, assess lenses for damage.	
4.12.	Lens Removal	
The lenses will be removed and stored in the following manner:
 
The OD and OS lenses will be stored wet (using saline solution) in separate glass vials with labels that minimally contain study number, date, subject number, and eye from which the lens was removed.
 
*The lenses will be shipped back to the Sponsor ambiently once the study has completed.
	
4.13.	Slit Lamp Biomicroscopy	
FDA Slit Lamp Classification Scale will be used to grade the findings.
 
Limbal and Bulbar Conjunctival Hyperemia findings and detailed Corneal Staining Assessment will be recorded using a more detailed scale for internal purposes only. Conjunctival hyperemia should be assessed using the 0.5 increment grading scale.
	
4.14.	Eye Rinse	The investigator or technician may rinse the subject's eyes with sterile saline.	

FINAL EVALUATION

The final evaluation will ordinarily take place immediately following the last scheduled follow-up visit per the study protocol. It may also take place at any point the subject discontinues the study or is terminated from the study.

Final Evaluation			
Step	Procedure	Details	
F.1	Final Exam Form	Indicate if the subject completed the study successfully. If subject discontinued from the study, indicate the reason.	
F.2	Subjective spherocylindrical Refraction	Perform bare-eye subjective spherocylindrical refraction with a phoropter and record the best	

Final Evaluation		
Step	Procedure	Details
		corrected distance visual acuity to the nearest letter (OD, OS, and OU).
F.3	Comments and Signature	Record any additional information on the page provided and sign the form.

7.3. Unscheduled Visits

If, during the investigation, a subject requires an unscheduled visit to the clinical site, the following information will be collected at a minimum:

- Chief complaint prompting the visit. If the reason is an adverse event, the applicable eCRF for the adverse event must be completed and subject record completed as appropriate
- Date and time of the visit and all procedures completed at the unscheduled visit
- Review of adverse event and concomitant medications
- Documentation of any test article dispensed or collected from the subject, if applicable
- Slit lamp findings (using the Slit Lamp Classification Scale)

If the Investigator withdraws a subject from the study, the final study visit case report forms must be completed indicating the reason(s) why the subject was withdrawn. The subject record must be completed documenting the date and primary reason for withdrawal and the study CRA notified.

Any ocular and non-ocular Adverse Events that are ongoing at the time of the study visit will be followed by the Investigator, within licensure, until they have resolved, returned to pre-treatment status, stabilized, or been satisfactorily explained. If further treatment i.e., beyond licensure is required, the subject will be referred to the appropriate health care provider.

The following information will be collected during an unscheduled visit.

Unscheduled Visit		
Step	Procedure	Details
U.1	Chief Complaints	Record the subject's chief complaints for reasons for the unscheduled visit.
U.2	Adverse Events and Concomitant Medications Review	Review any changes to the subject's medical history or concomitant medications from the previous study visit. Record any changes, and any adverse events.
U.3	Entrance VA	Record the entrance distance visual acuity (OD, OS and OU) to the nearest letter.
U.4	Subjective Sphero-cylindrical Refraction	Perform bare-eye subjective sphero-cylindrical refraction with a phoropter (adopt the maximum plus to maximum visual acuity (MPMVA) approach and use the duo-chrome test for binocular balancing) and record the best corrected distance visual acuity to the nearest letter (OD, OS, and OU).

Unscheduled Visit			
Step	Procedure	Details	
U.5	Slit Lamp Biomicroscopy	FDA Slit Lamp Classification Scale will be used to grade the findings. If the clearance of the fluorescein needs to be expedited, preservative-free rewetting drops may be instilled.	
U.6	Dispensing (if applicable)	Subject may be provided with additional lenses as needed to allow continuation in the study if applicable	
U.7	Exit Visual Acuity	Record the subject's exit distance visual acuity (OD, OS, and OU) to the nearest letter.	

7.4. Laboratory Procedures

Not Applicable

8. SUBJECTS COMPLETION/WITHDRAWAL

8.1. Completion Criteria

Subjects are considered to have completed the study if they:

- provided informed consent
- they are eligible
- completed all scheduled visits.

8.2. Withdrawal/Discontinuation from the Study

A subject will be withdrawn from the study for any of the following reasons:

- Subject death during the study period
- Subject withdrawal of consent
- Subject not compliant to protocol
- Subject lost to follow-up
- Subject no longer meets eligibility criteria (e.g. the subject becomes pregnant)
- Subject develops significant or serious adverse events causing discontinuation of study lens wear
- Subjects who have experienced a Corneal Infiltrative Event (CIE)
- Investigator's clinical judgment regarding the subject safety reasons (that it is in the best interest of the subject to stop treatment)
- Subject misses any study visits
- Subject not compliant with study lens wear schedule
- Subject not successfully dispensed due to lack of efficacy and safety including poor vision, poor comfort or unacceptable fit.

For discontinued subjects, the Investigator will:

- Complete the current visit (scheduled or unscheduled)

- Complete the Final Evaluation, indicating the reason that the subject was discontinued from the study
- Record the spherocylindrical refraction with best corrected distance visual acuity
- Collect used test article(s) (worn or brought to the visit) from the subject and discard them, unless otherwise stated in Section 7.2
- Collect all unused test article(s) from the subject.

An additional subject will be enrolled if a subject discontinues from the study prematurely.

In cases where a subject is lost to follow-up, every possible effort must be made to contact the subject and determine the reason for discontinuation/withdrawal. The measures taken to follow up must be documented including two written attempts and a certified letter (or equivalent) as the final attempt.

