2.2. Endpoints

Primary Endpoint(s)

CLUE Comfort and Vision Scores:

The co-primary endpoints for this study are subjective assessment of comfort and quality of vision after 7 ± 2 days of wearing the study lenses as a daily disposable.

Subjective assessment of comfort and vision will be performed using the Contact Lens User Experience™ (CLUE) questionnaire. CLUE is a validated patient reported outcomes (PRO) questionnaire used to assess patient experience attributes of soft contact lenses (comfort, vision, handling, and packaging) in a US contact-lens wearing population between 18 and 65 years of age. CLUE composite scores are derived using Item Response Theory (IRT) and follow a normal distribution with a population average score of 60 (SD 20), where higher scores indicate a more favorable/positive response. A 5-point increase in an average CLUE score translates into 10% shift in the distribution of scores for the population of soft disposable contact lens wearers.

Secondary Endpoint(s)

Average daily wear time (in hours):

Average daily wear time will be calculated as the number of hours between subjects reported time of insertion and time of removal of the study lenses, on an average day, at 1-Week Follow-up evaluation.

Visual performance

Visual performance will be calculated as monocular contact lens-corrected distance visual acuity using a logMAR visual acuity scale. This will be evaluated under high luminance and high contrast conditions at 4 meters from Early Treatment Diabetic Retinopathy Study (ETDRS) charts at the 1-Week Follow-up visit.

Other Endpoint(s)

Slit Lamp Findings

Frequency and severity by eye of slit lamp findings (SLFs) including conjunctival injection, corneal edema, corneal neovascularization, corneal staining, tarsal abnormalities or any other complications. SLFs will be evaluated at fitting and post-fitting evaluation visits including unscheduled visits.

Subject's Reported Ocular Symptoms

Frequency and severity by eye of subject's reported ocular symptoms and problems with the study lens at fitting and post-fitting evaluation visits including unscheduled visits.

Lens Fitting characteristics

Frequency by eye of mechanical lens fitting characteristics including lens centration and lens movement and overall lens fitting acceptability at fitting and 1-week follow-up evaluations.

Lens wettability:

Frequency and Grade by eye of lens wettability at 1-Week Follow-up evaluation.

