2.3. Hypotheses

Primary Hypotheses:

There are two co-primary hypotheses in this study. Both of them must be met to satisfy the primary objective of the study.

1. The Test lens will be non-inferior to the Control lens with respect to overall CLUE comfort score at the follow-up visit. A non-inferiority margin of -5 points will be used.
2. The Test lens will be non-inferior to the Control lens with respect to overall CLUE vision score at the follow-up visit. A non-inferiority margin of -5 points will be used.

Secondary Hypotheses:

1. The Test lens will be non-inferior to the Control lens with respect to average daily wear time at 1-week follow-up visit. A non-inferiority margin of 1 hour will be used.

2. The Test lens will be non-inferior to the Control lens with respect to logMAR visual performance (using ETDRS visual acuity charts) at the follow-up visit. A non-inferiority margin of 0.05 logMAR will be used.

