1.25	Surface Deposits	Record any front and back surface lens deposits.	

Visit 1: Treatment 1 Lens Dispensing			
Step	Procedure	Details	
1.26	Exit VA	Record subjects' distance visual acuity, OD, OS, and OU to the nearest letter.	
1.27	Continuance	
For the subject to continue in the study, they must meet all three of the following criteria:
 
 • Visual acuity is 20/30 or better OD and OS • The lens fit is acceptable OD and OS • Investigator approval. 
If the Investigator does not approve the dispensing of the first study lens, then the study is terminated for that subject.
	
1.28	Dispense	
The lenses will be dispensed for a 5-9 day wearing period. During this time, they are required to wear the lenses at least 5 days and at least 8 hours per day that they are worn.
 
 • Dispense enough lenses to last the subject to their scheduled follow-up visit. Do not dispense extras* • The lenses will be worn as daily wear/daily disposable only • Rewetting drops are permitted if needed • A patient instruction booklet will be provided • Subjects will be scheduled for their 1-week follow-up visit • Subjects should be instructed to wear the study lenses to the follow-up visit and bring their habitual correction with them. 
* Note: In the event a lens is lost or damaged, the subject will return to the clinical site for replacement. As much as reasonably possible, a damaged lens and packaging should be returned to the clinical site (wet, if possible) and then returned to the Sponsor. If lens damage is present, complete the Product Quality Complaint Form. The lens will be stored in labeled vial with saline, and clearly differentiated from the other worn lenses that will be shipped back to the Sponsor.
	

VISIT 2

Subjects should attend wearing their study lenses.

Visit 2: Treatment 1 Follow-Up Visit			
Step	Procedure	Details	
2.1.	Adverse Events and Concomitant Medications Review	Review any changes to the subject's medical history or concomitant medications from the previous study visit. Record any changes, and any adverse events.	
2.2.	Wearing Time	Record the average wearing time and comfortable wearing time.	
2.3.	Compliance	Confirm compliance with the prescribed wear schedule.	
2.4.	Follow-Up Questionnaires (CLUE)	The subject will respond to the Follow-Up Questionnaire.	
2.5.	Subject Reported Ocular Symptoms	Subjects will respond to a verbal open-ended symptoms questionnaire.	

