14.3. Analysis Populations

Safety Population:

All subjects who were administered any test article excluding subjects who drop out prior to administering any test article. At least 1 observation should be recorded.

Per-Protocol (PP) Population:

All subjects who have successfully completed all visits and did not substantially deviate from the protocol as determined by the trial cohort review committee prior to database hard lock (Per-Protocol Population). Justification of excluding subjects with PDs in the Per-Protocol Population set will be documented in a memo to file.

Intent-to-Treat (ITT) Population:

All randomized subjects regardless of actual treatment and subsequent withdrawal from study or deviation from protocol.

Safety variables will be summarized on the safety population whereas efficacy variables will be summarized on the per-protocol and Intent-to-Treat population. The primary and secondary analyses will be conducted on both IIT and PP populations.

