14.4. Level of Statistical Significance

All planned analysis for this study will be conducted with an overall type I error rate of 5%. Type I error will be controlled for multiplicity across interim analysis and final analysis. The operating characteristics of this adaptive trial will be provided in the SAP.

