14.6. Secondary Analysis

Average Daily Wearing Time

Average daily wear time will be analyzed using the same Bayesian model described in the primary analysis.

The null and alternative hypotheses for non-inferiority of Test lens relative to Control are as follows:

$$H_0: \Delta < -1$$
$$H_A: \Delta \geq -1$$

where Δ is the mean difference in average daily wearing time between Test lens and Control lens (Test minus Control). Non-inferiority will be declared if the lower bound of the credible interval of the mean difference between Test and Control is greater than -1. Superiority will be declared if the lower bound of the credible interval of the mean difference between Test and Control is greater than 0. The superiority test will be performed only if non-inferiority is established.

Visual Performance

Monocular distance visual performance in logMAR scale will be analyzed using a Bayesian repeated measurement random-effects model to compare between Test and Control lenses. The regression model will include baseline values, lens type, lens wearing sequence and lens wearing period as fixed effects; and investigational site and patient as random effects. Other subject characteristics such as age, gender and will also be included as fixed effects when appropriate. Unstructured covariance matrix will be used to model the residual errors among observations within same eye and subject across wearing periods. Non-informative prior distributions will be used for the coefficients in the models as well as for the error terms. Independent vague normal $N(0,1000)$ priors will be used for the regression coefficients, inverse gamma $IG(0.001, 0.001)$ for the variance of the random effect site and inverse Wishart for the residual errors. The Metropolis sampler algorithm as implemented in the SAS MCMC Procedure will be used to carry out parameter estimation. Results will be reported as regression coefficient mean estimates with credible intervals.

The null and alternative hypotheses for non-inferiority of Test lens relative to Control are as follows:

$$H_0: \Delta > 0.05$$
$$H_A: \Delta \leq 0.05$$

where Δ is the mean difference in logMAR between Test lens and Control lens (Test minus Control). Non-inferiority will be declared if the upper bound of the credible interval of the mean difference between Test and Control is less than 0.05.

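### The per-protocol wear-time analysis can be selected on wear time itself, which pulls the difference toward zero and favours non-inferiority

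*Combined protocol and SAP*

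**What the plan says.** **Endpoint.** Section 2.2: "Average daily wear time will be calculated as the number of hours between subjects reported time of insertion and time of removal of the study"; the value describes a typical day and is taken at the 1-week follow-up. Section 2.3: "The Test lens will be non-inferior to the Control lens with respect to average daily wear time at 1-week follow-up visit", and "A non-inferiority margin of 1 hour will be used". Section 14.6: "Non-inferiority will be declared if the lower bound of the credible interval of the mean difference between Test and Control is greater than -1".

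**Minimum on the same variable.** At dispensing (Section 7.2, steps 1.28 and 3.23), "they are required to wear the lenses at least 5 days and at least 8 hours per day that they are worn". Section 1.2 also describes wear of at least 8 hours a day. Section 4.1 gives the 8 hours as advice, for a minimum of 6 days.

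**Check and consequence.** Steps 2.2 and 4.2 record wear time. Steps 2.3 and 4.3 then confirm compliance with the prescribed wear schedule. Section 8.2 says that a subject will be withdrawn for any listed reason, including "Subject not compliant with study lens wear schedule".

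**Analysis sets.** Section 14.3 defines per-protocol as "All subjects who have successfully completed all visits and did not substantially deviate from the protocol", the deviation being judged by the cohort review committee before database lock. Secondary analyses run on both the ITT and the per-protocol set, and neither is named as decisive. Section 14.9 rules out imputation.

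**The concern.** The variable tested for non-inferiority is also the variable on which subjects can be removed. A subject who manages only 6 or 7 hours with a lens has the outcome of interest, and on a natural reading of Section 8.2 leaves the study because of it. An average below 8 hours implies at least one worn day below 8 hours, so every such value breaches the dispensing requirement.

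The two periods differ. A subject withdrawn at Visit 2 cannot complete all visits and is out of the per-protocol set by definition. A subject short at Visit 4 has completed all visits and is excluded only if the committee judges the deviation substantial.

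If Test shortens wear, more Test than Control values lie below 8 hours. Removing those subjects moves the per-protocol difference toward zero, and non-inferiority is declared more often than the stated error rate allows.

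**Working it through.** **Nominal level.** Section 14.4 sets 5% overall without giving sidedness, and Section 14.6 gives no credible level. Table 6 (Section 14.2, CLUE only) settles what was used for power. For N = 150, correlation 0.5, SD 24:

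- SD of the difference = 24 × √(2 × 0.5) = 24; SE = 24/√150 = 1.960; noncentrality = 5/1.960 = 2.55.
- Paired t-test, 149 df: two-sided 5% gives 0.717, the tabulated value; one-sided 5% gives 0.815.

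All 18 cells of Table 6 reproduce at two-sided 5%. The nominal false non-inferiority rate is therefore taken as 2.5%.

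**Assumed inputs (not in the documents).** Control mean 12 h, SD 2.5 h for each lens, correlation 0.5, normal values, true difference exactly -1 h (Test mean 11 h). N = 150 and 250 come from Section 14.2. A normal-theory interval stands in for the credible interval.

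**Share below 8 h.** Control: Φ((8 − 12)/2.5) = Φ(−1.6) = 5.5%. Test: Φ((8 − 11)/2.5) = Φ(−1.2) = 11.5%.

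**False non-inferiority.** With m the mean difference among retained pairs and SE = SD/√(retained n), the rate is Φ((m + 1)/SE − 1.96). With no selection m = −1 and the rate is Φ(−1.96) = 2.5%.

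*Reading A: only Visit 2 withdrawals act.* Half the subjects wear Test first, half Control first. Loss = (5.5% + 11.5%)/2 = 8.5%. Shift in the mean = 0.5 × 2.5 × (φ(1.2) − φ(1.6))/(Φ(1.2) + Φ(1.6)) = 1.25 × (0.1942 − 0.1109)/1.830 = 0.057, so m = −0.943. The retained SD, by simulation, is 2.43.

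*Reading B: every pair with a value below 8 h is excluded.* By simulation, 14.7% of pairs are lost, m = −0.860 and SD = 2.32.

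| Reading | N | retained n | SE | (m + 1)/SE | false NI |
|---|---|---|---|---|---|
| A | 150 | 137 | 0.207 | 0.277 | 4.6% |
| A | 250 | 229 | 0.161 | 0.357 | 5.4% |
| B | 150 | 128 | 0.205 | 0.681 | 10.0% |
| B | 250 | 213 | 0.159 | 0.879 | 14.0% |

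Finite-sample t-interval simulations give 4.4% and 5.6% for A, and 10.0% and 14.0% for B.

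**Range.** Over Control means 11-14 h, SD 2-3 h, correlation 0.5-0.7 and both N:

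- Reading A: about 3% to 7%. If the two sequences are weighted equally, as a model with sequence and period terms tends to do, the central case becomes 5.0-6.0% and the upper end about 8%.
- Reading B: about 3% to 25%.

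The low ends belong to a Control mean of 14 h, where few values are near 8 h. The high ends belong to 11 h.

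**ITT.** The value that triggers withdrawal is recorded before the compliance check, and Section 8.2 has the current visit completed. Period 2 is then missing in a way that depends on an observed value. Over Control means 11-14 h and SD 2-3 h, with withdrawal on a period-1 value below 8 h and a likelihood-type estimator using all recorded data, the difference was −0.99 to −1.01 h in all 24 settings. False non-inferiority was 1.6-3.5% (1,500 trials per setting, so a simulation SE of about 0.4 points).

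**The case against.** **The link to 8 hours is inferred.** The Section 8.2 item names no hours. The Synopsis and Table 2 use wear schedule as a label for daily wear, and Section 4.1 only advises the 8 hours. This stands as a limit: the mechanism depends on reading the wear schedule to include the minimum. But steps 1.28 and 3.23 make it a requirement, the compliance check follows directly on the wear-time record, and Section 8.2 also lists general protocol non-compliance. No passage exempts this endpoint.

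**Visit 4 exclusion is not automatic.** Correct. Reading B is an upper case; Reading A is what follows from the definitions alone once the 8-hour link is accepted.

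**ITT is analysed as well.** A reader might infer that ITT is compromised too, because withdrawn subjects lose period 2 without imputation. The documents do not support that: the low value is kept, Visit 4 values stay in, and the planned repeated-measures model can use incomplete subjects. If success required both sets, ITT would hold the error near nominal. Section 14.3 does not say that it does.

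**Not every deficit is hidden.** A reader might also infer that all evidence of inferiority leaves the per-protocol set. It does not. A loss lying wholly above 8 hours, such as 14 h against 12.5 h, remains visible.

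**The endpoint is secondary.** The study objective rests on the CLUE co-primaries, and Section 14.1 defers detail to a stand-alone SAP. Both facts limit the weight of the point, but neither answers it.

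**Conclusion.** The point holds for the per-protocol analysis of average daily wear time, provided the wear schedule in Section 8.2 includes the 8-hour minimum. That set is then selected on the endpoint value, and the direction favours non-inferiority when Test is worse. In the assumed central case the error roughly doubles (about 4.5-5.5% against 2.5%) from Visit 2 withdrawals alone, and reaches about 10-14% if the committee also excludes every Visit 4 short wearer. The size depends on how close typical wear lies to 8 hours, and the documents give no figure for that; at a Control mean of 14 h with SD 2 h the effect is negligible. ITT is largely protected as long as incomplete subjects stay in the model. The remaining gap is that no population is named as decisive, so a per-protocol claim could stand alone. It is worth correcting before database lock, as a matter for a secondary endpoint.

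**What to change.** In Sections 14.3 and 14.6, state that:

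- every wear time recorded at Visits 2 and 4 enters both the ITT and the per-protocol wear-time analysis whatever its value, including values from subjects withdrawn for short wear;
- daily hours below 8 is not a per-protocol exclusion for this endpoint;
- the share of values below 8 hours is reported by lens.

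Naming which population decides for wear time would close the remaining gap.

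Separately, the sponsor must reconcile Section 4.1 (advice, 6 days), steps 1.28 and 3.23 (requirement, 5 days) and the wear-schedule item in Section 8.2. Which wear or withdrawal rule should apply is for the sponsor.

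The cost is a few sentences and one summary line. The downside is that the wear-time per-protocol set will include some short-wear subjects and so will differ from the per-protocol set used for other endpoints.
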